Protocol Component	Description under target trial	Description under Emulation
Eligibility Criteria	Adult inpatients receiving B-lactam therapy for culture confirmed monomicrobial invasive GAS between who can be randomized within 72h of index culture	Adult inpatients receiving B-lactam therapy for culture confirmed monomicrobial invasive GAS between the years 2015-2021 in the PINC AI™ dataset who receive anti-toxin within 3 days of index culture.
Treatment strategies	B-lactam therapy as primary therapy for GAS started within (+/-) 3 days of index GAS culture and continued for a minimum of 3 consecutive days. Adjunctive anti-toxin (clindamycin vs. linezolid) therapy started within (+) 3 days of culture.	Same as target trial.
Assignment procedures	
Patients will be randomly assigned within 3 days of culture (grace period) to clindamycin vs. linezolid. Investigators and patients and will be aware of the strategy to which they have been assigned (pragmatic, unblinded, open-label non-inferiority).
 
Switching between linezolid and clindamycin will not be permitted under the protocol.
	
Patients will be assigned to the anti-toxin therapy compatible with their observed treatment. Difference in baseline characteristics and confounding by indication will be addressed through the creation of a propensity weighted cohort.
 
Those who received both agents within the eligibility period will be excluded.

Follow up period	Starts at time of randomization (anti-toxin initiation) and ends at death, discharge to hospice, loss to follow up or 90 days, whichever occurs earliest.	Starts at time of anti-toxin initiation and ends at death, discharge to hospice or discharge from the hospital to home or facility or administrative censorship on Jan 31 st 2022.
Outcome	
Primary outcome: Time to all-cause mortality (or discharge to hospice) censored at 90 days.
 
Secondary outcome: infection attributable 90-day mortality, all-cause in-hospital mortality, 90-day disease reoccurrence, length of stay following anti-toxin administration among survivors, occurrence of CDI
	
Primary outcome: All-cause in-hospital mortality (or discharge to hospice)/ time to death (days).
 
Secondary outcome: Length of stay following anti-toxin administration among survivors, occurrence of CDI requiring treatment following anti-toxin administration.

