requiring treatment following anti-toxin administration up to 90 days, occurrence of serotonin surge syndrome while on therapy.

Causal contrast of interest	Intention-to-treat effect; per-protocol effect.	Observational analog to Intention-to-treat effect and per-protocol effect.
Analysis plan	Intention-to-treat and per protocol effects estimated via comparison of adjusted 90 day in-hospital mortality risk assigned to each treatment strategy.	
Intention-to-treat and per protocol effects estimated via comparison of adjusted in-hospital mortality risk assigned to each treatment strategy.
 
To account for confounding by indication a propensity score (PS) will be generated based on the probability of receiving linezolid using the patient and center level variables selected a priori based on clinical judgment, . Overlap weighting on a propensity-score between the two groups will be performed with downstream adjustment for ICU stay , shock and debridement/source control.

Abbreviations: CDI: Clostridioides difficile infection; GAS: Group A streptococcus.

The study was designed in accordance with the trial emulation approach described by Hernán and Robins¹⁹. The study aims to emulate a hypothetical target pragmatic multi-center, non-blinded trial.

Eligibility

Adult inpatients patients (≥ 18 y of age) with culture confirmed proven or probable (see below) invasive monomicrobial GAS in the PINC AI™ database between 2015-2021 who receive a β -lactam for a minimum of 3 days within 3 days of culture will be eligible for inclusion in the emulated trial. Patient will be included if they then receive anti-toxin therapy within 3 days of culture being drawn, as long as B-lactam therapy has been initiated prior or on the same day as antitoxin therapy.

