Proven and probable invasive GAS definitions will be adapted from the CDC ABCs case definition (<https://www.cdc.gov/abcs/methodology/case-def-ascertain.html>) using a previously used algorithm compatible with EHR data which incorporates ICD-codes³. Proven invasive GAS infection will be defined as GAS isolated from a normally sterile site, such as blood, cerebrospinal fluid, pleural fluid, peritoneal fluid, pericardial fluid, bone, joint/synovial fluid, or internal body site (e.g., lymph node, brain) OR GAS isolated from a wound culture and accompanied by necrotizing fasciitis or streptococcal toxic shock syndrome. Probable invasive GAS infection is defined as the isolation of GAS from a non-sterile site in patients with either an ICD-10 code that matches the clinical infection syndrome (eg ICD-10 for lower respiratory infection and BAL culture with GAS) or a non-specific streptococcal infection code. These include lower respiratory, musculoskeletal, genitourinary and/or skin and soft tissue samples as well other miscellaneous deep-seated infections (eg retropharyngeal abscess). Previously identified ICD-9 codes³ will be cross walked to ICD-10 codes manually with additional manual de-novo search for compatible ICD-10 codes. Final codes and culture site classification will be adjudicated by two infectious diseases clinicians.

Inclusion Criteria

- Adult inpatients patients (≥ 18 y of age)
- Monomicrobial Group A streptococcus invasive infection
- Primary therapy with a B-lactam agent (initiated before or on same day as adjunctive anti-toxin therapy)

Exclusion Criteria

Patient will be excluded if they have any of the following :

- Patients with a polymicrobial GAS culture
- Patients who allocated to the linezolid arm but have a documented linezolid resistant isolate
- Patient with concomitant MSSA/MRSA invasive infection (+/- seven days of index GAS eligibility culture)
- Patients who receive both anti-toxin agents (violation of protocol)
- Patient who don't complete at least 3 days of B-lactam (violation of protocol)

Primary Outcome measure:

in-hospital mortality defined as death during hospitalization or discharge to hospice.

Secondary outcome measures:

- Length of stay among survivors

- *Clostridioides difficile* infection

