 - Description: *C. difficile* positive (PCR or antigen) result within same encounter downstream of the antitoxin therapy within 30 days and/or presence of a non present on admission (POA) *C. difficile* diagnosis code in conjunction with receipt of *C. difficile* therapy (PO/rectal vancomycin or PO fidaxomicin or IV metronidazole)

Statistical Analysis Plan

To account for confounding by indication a propensity score (PS) will be generated based on the probability of receiving linezolid using the patient and center level variables. Variables thought to be associated with a clinician's decision to initiate adjunctive treatment with linezolid (vs. clindamycin) and with mortality will be selected for inclusion. Overlap weighting on a propensity-score between the two groups will be performed with downstream adjustment for ICU stay, shock and debridement/source control. To take the clustered data structure into account, matching on center will be attempted if feasible, if not, propensity scores will be calculated using a mixed effects model with hospital as a random effect. Covariate balance between the two groups before and after generation of the weighted cohorts will be assessed by examining the standard mean difference for variables across the exposure categories.

Power calculation

Because no randomized clinical trials have previously compared adjunctive treatment options for GAS, the sample size estimation was derived from the largest retrospective study available³. In that study the overall in hospital mortality in adjunctive clindamycin group 6.5% in the propensity matched cohort. A published abstract, the only other published clinical data on the topic, found mortality between linezolid (n=26) and clindamycin (n=26) groups to be similar (clindamycin 11.5% and linezolid 7.7%)²¹. This was confirmed by preliminary exploration of GAS blood stream infection cases in our dataset (clindamycin 10%, linezolid 12%).

Based on a mortality rate of 6.5% in the both groups as the most conservative estimate and a noninferiority margin of 5% with 1:4 allocation ratio, 1035 patients (828 clinda + 207 Linezolid) will be needed in total to achieve 80% power with a 2-sided α level of 0.05, allowing for 10% dropout. A 5% noninferiority margin was chosen as the maximal difference in mortality between treatments that would be clinically acceptable, by consultation with infectious disease, critical care specialists within the study team.

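### The CDI outcome bars infection present on admission only in its diagnosis-code branch, so pre-existing CDI that tests positive after anti-toxin start is counted as a new event

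*Combined protocol and SAP*

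**What the plan says.** The combined protocol and SAP defines the outcome under Secondary outcome measures, Clostridioides difficile infection (Description). The governing wording is "positive (PCR or antigen) result within same encounter downstream of the antitoxin therapy within 30 days and/or presence of a non present on admission". It gives two routes to an event.

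- **Test route:** a positive C. difficile test after anti-toxin start, in the same admission and no more than 30 days later.
- **Code route:** introduced by and/or, a code that is not POA, with the therapy condition written as "diagnosis code in conjunction with receipt of" C. difficile therapy (oral or rectal vancomycin, oral fidaxomicin or IV metronidazole).

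Table 1 (Outcome, emulation column) describes the outcome more briefly, as "occurrence of CDI requiring treatment following anti-toxin administration".

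On timing, Table 1 says of follow-up: "Starts at time of anti-toxin initiation and ends at death, discharge to hospice or discharge from the hospital". The Eligibility section adds: "Patient will be included if they then receive anti-toxin therapy within 3 days of culture being drawn".

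The exclusion list opens with "Patient will be excluded if they have any of the following" and has five entries. None concerns CDI. The sensitivity and subgroup analyses do not address it either.

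**The concern.** Because the code route is limited to CDI that was not POA, the authors evidently want to count new CDI. The test route has no matching limit. It needs only a positive result after anti-toxin start, with no minimum interval and no earlier negative test.

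Anti-toxin starts within 3 days of the culture. For infections cultured at presentation, that is also when symptoms present at admission are being worked up. A patient admitted with diarrhoea, given the first dose on day 0 and found positive on a stool test on day 1 would be an event. So would a patient with known CDI before anti-toxin start who is retested and positive a few days later.

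CDI is the only adverse-event outcome kept in the emulation; serotonin syndrome is listed only for the target trial. Events that predate the first dose say nothing about which drug causes more CDI, and they dilute or distort that comparison.

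**Working it through.** **Step 1: does the rule count pre-existing CDI?** Let A = positive test after anti-toxin within the window, B = C. difficile code not flagged POA, T = CDI therapy received. Pre-existing CDI that tests positive after the first dose has A = 1, B = 0. The same illness found only through a POA code has A = 0, B = 0.

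| Reading of the rule | A=1, B=0, untreated | A=1, B=0, treated | A=0, B=0 |
|---|---|---|---|
| A or (B and T): literal text | event | event | no event |
| (A or B) and T: closest to Table 1 | no event | event | no event |
| A and B and T | no event | no event | no event |

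Only the third reading never counts the pre-existing case, and it contradicts the and/or. The gap is therefore separate from the question of whether treatment is required for a positive test.

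**Step 2: what do such events do to the contrast?** There is no plan figure to reproduce, because the documents give no CDI rates. The following inputs are assumptions:

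- p, CDI present at anti-toxin start: 0.3% to 1%
- t, share of these testing positive afterwards: 30% to 60%
- I, true new CDI in the clindamycin arm: 1% to 2%
- true linezolid/clindamycin risk ratio: 0.50

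Observed risk in an arm ≈ I + e, where e = p × t. So e runs from 0.003 × 0.3 = 0.0009 to 0.01 × 0.6 = 0.006.

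With e equal in both arms:

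- Mildest corner (I = 2%): observed ratio = (0.010 + 0.0009)/(0.020 + 0.0009) = 0.0109/0.0209 = 0.52. False share in the clindamycin arm = 0.0009/0.0209 = 4%.
- Strongest corner (I = 1%): observed ratio = (0.005 + 0.006)/(0.010 + 0.006) = 0.011/0.016 = 0.69. False share in the clindamycin arm = 0.006/0.016 = 38%.
- Risk difference: (I_L + e) − (I_C + e) = I_L − I_C, so e cancels. If patients with existing CDI cannot also have a new episode, the difference is multiplied by (1 − p), a relative change of at most 1%.

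With e unequal, the risk difference shifts by e_L − e_C and the ratio can move either way.

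**Step 3: how many events?** The Power calculation section plans 828 clindamycin and 207 linezolid patients. False events: 828 × 0.0009 = 0.7 to 828 × 0.006 = 5.0 on clindamycin, and 207 × 0.0009 = 0.2 to 207 × 0.006 = 1.2 on linezolid. True events at 2% and 1%: 828 × 0.02 = 16.6 and 207 × 0.01 = 2.1. The unweighted standard error of the log ratio is √(1/2.07 − 1/207 + 1/16.56 − 1/828) = 0.733, so the 95% interval around 0.50 is 0.50 × exp(±1.96 × 0.733) = 0.12 to 2.1.

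**The case against.** Several replies have force.

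- **The test route has its own time gate.** The result must follow anti-toxin, and the code route states no date, so the POA wording may simply supply the timing that codes lack. This narrows the gap to CDI present on admission and first tested, or retested, after the first dose. It does not close it: the time of a result is not the time of onset.
- **Table 1 ties the outcome to treatment after anti-toxin.** This adds a treatment condition but does not require freedom from CDI at the start. Treated pre-existing cases still count (Step 1).
- **The propensity score may balance prior CDI.** The covariates are not listed, so this cannot be checked. Balance would make false events about equally common in the weighted arms, but they would still be scored as outcomes.
- **The outcome is secondary and imprecise.** This stands. The assumed shift from 0.50 to at most 0.69 lies well inside the interval in Step 3.

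A reader might infer two stronger claims that the documents do not support. The first is that the comparison is always pulled toward no difference. With equal frequency, that is true of a ratio but not of a risk difference. No effect measure is named for CDI, and the mortality comparison is framed in terms of risk with a 5% margin.

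The second is that false events collect in the linezolid arm because clinicians avoid clindamycin in patients with CDI. Nothing in the documents says so. A result that arrives after the drug is chosen cannot have driven the choice, and known cases count only if retested positive. A figure for this would need an assumed imbalance with no basis in the plan.

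**Conclusion.** The defect stands as one of outcome definition and does not depend on any assumed rate. Followed literally, the rule scores pre-existing CDI as new when it reaches the data through a test, and not when it reaches them only through a POA code. It does so even if treatment is required on both routes.

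The numerical effect is unknown and probably small. The range of 0.52 to 0.69 for a true ratio of 0.50 rests wholly on the assumed rates and on equal frequency in the two arms. Under the same assumptions a risk difference is essentially unshifted, though noisier. Unequal frequency could bias either measure, in a direction the documents do not let one predict. The mortality analysis, the non-inferiority margin and the total of 1035 are untouched. It is worth correcting because it affects the emulation's only adverse-event outcome and the correction is cheap.

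**What to change.** For the CDI outcome only, define the risk set as patients without CDI at anti-toxin start. Exclude those with either:

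- a C. difficile diagnosis code flagged POA; or
- a positive C. difficile test in the encounter on or before the day of anti-toxin start.

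Do not exclude on drug charges alone: the definition accepts IV metronidazole as CDI therapy, and that drug is not specific to CDI. Among the remaining patients, a positive test after anti-toxin start counts, including when no CDI code is recorded. State whether tests are dated by collection or by result. Separately, reconcile the treatment condition between Table 1 and the outcome description.

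The cost is one sentence in the definition and one filter on test dates and POA flags, which the rule already uses. A few patients leave the CDI analysis, and the mortality cohort is unchanged. One limit remains: pre-existing CDI with no POA code and no earlier positive test would still be counted.

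### The code-based limb of the CDI outcome accepts metronidazole only by the IV route, so coded, untested CDI treated with oral metronidazole alone is scored as no CDI

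*Combined protocol and SAP*

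**What the plan says.** In Table 1 (Outcome row, emulation column) one of the two secondary outcomes is "occurrence of CDI requiring treatment following anti-toxin administration". No agent or route is named there.

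The operational definition is under Secondary outcome measures, *Clostridioides difficile* infection. It has two limbs:

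- **Test limb:** a "positive (PCR or antigen) result within same encounter downstream of the antitoxin therapy within 30 days". As written, it carries no treatment condition.
- **Code limb:** a *C. difficile* "diagnosis code in conjunction with receipt of" *C. difficile* treatment. The code must not have been present on admission, and the qualifying treatments are listed as "therapy (PO/rectal vancomycin or PO fidaxomicin or IV metronidazole".

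The limbs are joined by and/or ("within 30 days and/or presence of a non present on admission (POA" and so on), so on the plain reading either one is enough. Vancomycin is accepted orally or rectally and fidaxomicin orally, but metronidazole only intravenously. No reason is given for the restriction. None of the analyses listed under Sensitivity analysis varies the CDI definition.

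**The concern.** The list treats metronidazole as evidence of treated CDI but leaves out its oral form, while it accepts the oral forms of the other two drugs. A coded, hospital-onset CDI treated with oral metronidazole alone fits Table 1's description of the outcome and fails the code limb. If no qualifying positive test is on record either, the patient is analysed as CDI-free. This is a stated rule that misclassifies some patients; it is not just a missing detail.

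It deserves a line because CDI is the only adverse-event outcome besides mortality in the emulation column. Events will also be few in the smaller arm: the power calculation plans 207 linezolid patients against 828 on clindamycin. An undercount makes any absolute CDI difference between the drugs look smaller than it is.

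**Working it through.** The documents state no CDI rate, event count or power for this outcome, so there is no planned figure to reproduce. The check is one of logic, followed by a range under labelled assumptions.

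**Step 1. The rule.** CDI = (positive test) OR (code not present on admission AND listed therapy). Applied to a patient with such a code whose only CDI treatment is oral metronidazole:

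| Positive PCR or antigen in the window? | Test limb | Code limb | Scored as | Fits Table 1's wording? |
|---|---|---|---|---|
| Yes | met | not met | CDI | yes |
| No | not met | not met | no CDI | yes |

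Only the second row is misclassified.

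**Step 2. Share of events missed.** Let c be the share of true CDI that is coded without a qualifying positive test, and m the share of those patients given oral metronidazole alone. Then the share missed is c × m. Neither quantity is in the documents; the ranges below are assumptions.

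| c | m = 5% | m = 10% | m = 20% | m = 40% |
|---|---|---|---|---|
| 5% | 0.25% | 0.5% | 1% | 2% |
| 10% | 0.5% | 1% | 2% | 4% |
| 20% | 1% | 2% | 4% | 8% |
| 30% | 1.5% | 3% | 6% | 12% |

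**Step 3. Effect on the comparison if the loss is equal in both arms.** Take assumed true CDI risks of 3% (clindamycin) and 1.5% (linezolid) with the planned 828 and 207 patients. Each observed risk is the true risk × (1 − share missed).

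| Share missed | Expected events, clindamycin | Expected events, linezolid | Risk ratio | Risk difference |
|---|---|---|---|---|
| 0 | 24.84 | 3.10 | 2.0 | 1.50 points |
| 2% | 24.34 | 3.04 | 2.0 | 1.47 points |
| 6% | 23.35 | 2.92 | 2.0 | 1.41 points |
| 12% | 21.86 | 2.73 | 2.0 | 1.32 points |

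The factor (1 − share missed) cancels from the ratio and multiplies the difference.

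**Step 4. Scale against sampling error.** The unweighted standard error of the risk difference is √(0.03 × 0.97/828 + 0.015 × 0.985/207) = 1.03 points. The largest shift above is 1.50 − 1.32 = 0.18 points.

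**The case against.** The strongest reply is that the operational definition is entitled to be narrower than Table 1's summary phrase. A shorter drug list trades sensitivity for specificity, the test limb recovers much of what the code limb misses, and the remaining effect is small next to sampling error. Most of this stands, and it limits the size of the point. It does not explain the list itself. Specificity is not an evident reason to leave out the oral form, because the code requirement applies in any case and the listed IV form can also be given for reasons other than CDI.

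A reader might draw three stronger conclusions that the documents do not support.

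- **Every coded patient on oral metronidazole alone is lost.** On the plain reading, a positive test in the window counts whatever the treatment. All such patients would be lost only if and/or meant that both limbs are required, or if Table 1's treatment condition were applied to the test limb with the same drug list. The text does not say either, although it should make clear how the two places fit together.
- **Sensitivity could be as low as one half.** If t is the share of CDI caught by the test limb and s the share of the rest on oral metronidazole alone, sensitivity is t + (1 − t)(1 − s). A value of 0.50 arises with s = 0.5 and t = 0, so the test limb would have to catch nobody. Eligibility requires a positive GAS culture, so microbiology results exist for the whole cohort. That does not prove that every *C. difficile* test is captured, but t = 0 is not a reasonable bound. With t = 0.8 and the same s, sensitivity is 0.8 + 0.2 × 0.5 = 0.90.
- **The clindamycin-linezolid ratio is biased.** This needs three things together: oral metronidazole use for CDI changed over 2015-2021, the mix of the two drugs changed over the same years, and the weighting left calendar time unbalanced. The documents show none of these. The SAP does not list its propensity-score variables, so whether year is among them is unknown. As an illustration only, let s be 0.6 in early years and 0.2 later, with 45% of clindamycin and 25% of linezolid patients early. Mean s is then 0.45 × 0.6 + 0.55 × 0.2 = 0.38 and 0.25 × 0.6 + 0.75 × 0.2 = 0.30. With t = 0.8, a true linezolid/clindamycin risk ratio of 1.0 would appear as (1 − 0.2 × 0.30)/(1 − 0.2 × 0.38) = 0.940/0.924 = 1.02.

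**Conclusion.** The point holds in a limited form. Patients with a CDI code not present on admission, oral metronidazole alone and no qualifying positive test are scored as CDI-free, contrary to Table 1's description of the outcome. The direction is an undercount. Its size cannot be obtained from the documents; the 0.25-12% range rests wholly on the assumed shares, and the event counts also rest on assumed CDI risks of 3% and 1.5%. An equal loss in both arms attenuates the absolute difference and not the ratio. Bias in the ratio is a conditional possibility only. This is a minor defect in one limb of one secondary outcome; the primary outcome, the noninferiority margin and the sample size do not depend on it.

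**What to change.** For outcome ascertainment only, add oral metronidazole started after the anti-toxin to the qualifying therapies in the code limb, and keep the requirement for a CDI code not present on admission. In the same edit, align the definition with Table 1 by stating whether a positive test alone qualifies or treatment is also required. If the IV-only restriction is deliberate, give the reason.

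The cost is one line in the outcome definition and one more drug and route in the pharmacy query. The downside is that a few coded patients given oral metronidazole for another reason would be counted. The code requirement limits this, and the IV form already on the list carries the same risk. The change concerns how CDI is counted in the dataset and says nothing about how it should be treated.

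### The propensity-score rule selects covariates by their link to agent choice and mortality only, so the CDI comparison can be confounded, and CDI that precedes anti-toxin start can be counted as an outcome

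*Combined protocol and SAP*

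**What the plan says.** **Covariate selection.** The Statistical Analysis Plan section gives the purpose: "To account for confounding by indication a propensity score (PS) will be generated based on the probability of receiving linezolid". Variables related to the "decision to initiate adjunctive treatment with linezolid (vs. clindamycin) and with mortality will be selected for inclusion". The Analysis plan row of Table 1 adds only that these are "patient and center level variables selected a priori based on clinical judgment". No list of variables is given.

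**Further adjustment.** After overlap weighting the plan makes a "downstream adjustment for ICU stay, shock and debridement/source control". The effect measure in Table 1 is written for in-hospital mortality. No model, covariate set or balance check is described for CDI.

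**The outcome.** The emulation column of Table 1 lists "occurrence of CDI requiring treatment following anti-toxin administration" as a secondary outcome. The definition under Secondary outcome measures has two routes joined by and/or:
- a positive PCR or antigen result "within same encounter downstream of the antitoxin therapy within 30 days";
- a CDI diagnosis code that was not present on admission (POA), together with CDI therapy.

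**Eligibility and other analyses.** None of the five exclusion criteria concerns earlier or current CDI. No sensitivity or subgroup analysis mentions it.

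**The concern.** A confounder is defined relative to an outcome. A variable that steers the choice between clindamycin and linezolid and predicts CDI, but is not thought to predict death in hospital, does not meet the stated rule and can be left out. CDI history is the obvious candidate. The three downstream covariates describe severity and source control and would not stand in for it. Standardised mean differences could look excellent for every variable in the score while CDI history stayed unbalanced, because overlap weighting guarantees nothing for variables outside the score.

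The second issue is the risk set. If patients with CDI at time zero stay in the analysis and can be counted as events, the outcome mixes existing disease with new disease. If such patients collect in one arm, both problems push the estimate in the same direction. What is at stake is the safety half of the comparison between the two agents.

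**Working it through.** **1. Is there a CDI figure to reproduce?** No. The documents give no CDI risk, no prevalence of prior CDI and no expected effect. The sample size (828 clindamycin + 207 linezolid) is for mortality. The first part of the check is therefore a reading of the text, and the sizes below rest on assumptions.

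**2. What each route does with CDI that precedes anti-toxin start**

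| Patient | Test route | Code route |
|---|---|---|
| CDI on admission, repeat positive test after anti-toxin | Counts: no earlier negative test or washout is required | Does not count (POA) |
| CDI arising in hospital before anti-toxin, treated, no later test | Does not count | Counts as written: not POA, and no timing is stated |
| CDI arising after anti-toxin | Counts if tested positive within the window | Counts if coded not POA and treated |

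Because the routes are joined by and/or, the first two patients can both be counted. Table 1 places CDI after anti-toxin administration. That would exclude the second patient if it governs, but the detailed definition does not repeat it for the code route.

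**3. Possible size of confounding.** Assume no drug effect. Let pL and pC be the prevalence of prior CDI in the weighted linezolid and clindamycin arms, and R the relative risk of CDI given prior CDI. The baseline risk cancels:

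spurious ratio = [1 + pL(R − 1)] / [1 + pC(R − 1)]

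| pL vs pC (assumed) | R = 3 | R = 5 | R = 10 |
|---|---|---|---|
| 2% vs 2% | 1.00 | 1.00 | 1.00 |
| 3% vs 1% | 1.06/1.02 = 1.04 | 1.12/1.04 = 1.08 | 1.27/1.09 = 1.17 |
| 5% vs 2% | 1.10/1.04 = 1.06 | 1.20/1.08 = 1.11 | 1.45/1.18 = 1.23 |
| 10% vs 2% | 1.20/1.04 = 1.15 | 1.40/1.08 = 1.30 | 1.90/1.18 = 1.61 |

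The same in absolute risks, assuming CDI in 15% with prior CDI and 2% without:
- Clindamycin, prior CDI 3%: 0.03 × 0.15 + 0.97 × 0.02 = 2.39%.
- Linezolid, prior CDI 10%: 0.10 × 0.15 + 0.90 × 0.02 = 3.30%; ratio 1.38.
- Linezolid, prior CDI 5%: 0.05 × 0.15 + 0.95 × 0.02 = 2.65%; ratio 1.11.

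**4. Could it mask or reverse a difference?** Take an assumed true ratio of 0.70 for linezolid. With 5% vs 2% and R = 5 the observed ratio is 0.70 × 1.11 = 0.78. With 10% vs 2% and R = 10 it is 0.70 × 1.61 = 1.13. Reversal occurs only at the extreme of the assumed range.

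**5. Size against precision.** At an assumed CDI risk of 1% to 3%, 207 linezolid patients give 2.1 to 6.2 events, and all 1035 patients give 10 to 31. In the 1.38 scenario the linezolid arm would have 207 × 3.30% = 6.8 events rather than 207 × 2.39% = 4.9, an excess of about two.

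**The case against.** The strongest reply is that this criticises silence. The rule permits CDI history to be left out but does not require it: it could enter if judged related to mortality, and Table 1 speaks of clinical judgment without a mortality filter. The documents never say which weights or model apply to CDI, so use of the mortality score for CDI is itself an inference. They also never say that clinicians choose between these agents on CDI history. The only reason discussed for preferring linezolid is clindamycin resistance. Acid suppression and recent antibiotic exposure confound only if they also affect agent choice, which the documents do not show. All prevalences and relative risks above are assumed, and correlated covariates in the score might remove part of any imbalance.

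Much of this stands. A reader might infer that the CDI comparison is confounded; the documents support only that it can be. A reader might also infer that nothing guards against existing CDI. That is wrong too: the POA condition protects the code route against CDI present on admission, and the test route requires a result after anti-toxin therapy.

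The reply does not remove the gap. The selection rule is an explicit statement that names one outcome, and nothing else in the document supplies a CDI covariate, model or exclusion. A team could follow the plan exactly and leave CDI confounders unbalanced. The gap in the two outcome routes does not depend on any view about prescribing.

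**Conclusion.** The point holds as a weakness in the prespecified analysis of a secondary safety outcome. It should be fixed, but it does not threaten the primary mortality analysis.

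- **Covariates:** the rule lets CDI confounders be omitted. Whether bias follows depends on whether CDI history or risk affects agent choice, which the documents leave open. Under the assumed inputs the spurious ratio is 1.00 to about 1.6, against linezolid if CDI-prone patients are steered towards it. With few expected events, random error is likely to be larger than the milder of these biases.
- **Outcome definition:** the test route lets a repeat positive from pre-existing CDI count, and the code route as written lets CDI arising in hospital before anti-toxin count, which disagrees with Table 1. This follows from the text alone; the number of patients affected is unknown.

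**What to change.** 1. **Rule.** Replace the mortality-only condition with: variables associated with agent choice and with mortality or CDI. List the variables before outcomes are examined.
2. **Adjustment.** Add the baseline CDI predictors that the database holds (prior CDI, antibiotic exposure before time zero) to the single overlap-weighted score, or to the CDI outcome model. Report their balance before and after weighting. A second score used only for CDI is less attractive, because overlap weights define the target population and harm would then be estimated in a different population from mortality.
3. **CDI risk set.** For the CDI analysis only, remove patients with a POA CDI code, or with a positive test or CDI-directed therapy on or before the day of anti-toxin start.
4. **Definition.** Require CDI onset after anti-toxin start on both routes, so that the definition agrees with Table 1.

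**Cost.** Wording changes, a few derived variables and extra rows in the balance table. The CDI risk set becomes slightly smaller, CDI history is limited by the database look-back, and the few events leave room for only a few extra terms in a CDI outcome model. The mortality cohort keeps every patient. Its weights would shift if CDI predictors enter the shared score, and would not if they enter only the CDI outcome model.
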